2. STUDY DESIGN

2.1. Summary of Study Design

The LIBERTY 1 and LIBERTY 2 studies are two replicate, randomized, double-blind, placebo-controlled phase 3 studies evaluating the efficacy and safety of relugolix 40 mg in combination with E2 1 mg/NETA 0.5 mg in women with heavy menstrual bleeding associated with uterine fibroids (MVT-601-3001, MVT-601-3002). Patients with heavy menstrual bleeding associated with uterine fibroids — as evidenced by a menstrual blood loss (MBL) volume of ≥ 80 mL per cycle for 2 cycles or ≥ 160 mL during one cycle, as measured by the alkaline hematin method during the screening period — who met other eligibility criteria were randomly assigned (1:1:1) to 1 of the 3 treatment arms:

- Group A (relugolix + E2/NETA): relugolix 40 mg once daily co-administered with E2 1 mg/NETA 0.5 mg for 24 weeks;
- Group B (relugolix + delayed E2/NETA): relugolix 40 mg once daily for 12 weeks followed by relugolix 40 mg once daily co-administered with E2 1 mg/NETA 0.5 mg for 12 weeks;
- Group C (placebo): placebo for 24 weeks

Randomization was stratified as follows:

- Geographic Region: North America versus Rest of World;
- Mean screening MBL volume using alkaline hematin method: < 225 mL versus ≥ 225 mL.

The primary endpoint for both trials is the proportion of women receiving relugolix + E2/NETA (Group A) versus placebo (Group C) who achieve BOTH a MBL volume of < 80 mL AND at least a 50% reduction from Baseline in MBL volume over the last 35 days of treatment, as measured by the alkaline hematin method.

This study includes a screening period (up to ~ 13 weeks), a randomized treatment period (24 weeks), and a safety follow-up period (~ 30 days). During the screening period, diagnoses of uterine fibroids are confirmed by centrally reviewed transvaginal ultrasound. Women with iron-deficient microcytic anemia and hemoglobin ≥ 8 g/dL and ≤ 10 g/dL during the screening period are treated with oral or parenteral iron replacement therapy. After randomization, patients begin double-blinded study drug treatment for 24 weeks.

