Abbreviations: eDiary, electronic diary; FP, feminine product; EOT, end of treatment; MBL, menstrual blood loss; N/A, not available.

^a Defined as those patients who meet the following criteria: eDiary entry rate > 70% and no more than 3 consecutive days and no more than 5 days of bleeding/spotting and use of feminine product reported on the eDiary over the Week 24/EOT visit window (see [Table 5](#)).

7.3.6. Mixed-Effects Model for Imputing Missing or Partially Missing MBL Volume at Week 24/EOT

For the primary analysis, patients with missing MBL volumes at Week 24/EOT will be identified per missing data handling rules as described above. For imputing missing data for the primary analysis, a mixed-effects model approach will be used, as the mixed-effects approach may better describe the effects of a hormonal treatment (such as suppression of the hypothalamic-pituitary-ovarian axis by GnRH antagonists).

Specifically, a mixed-effects model with repeated measures of MBL volumes at multiple time points (Weeks 4, 8, 12, 16, 20 and 24) will be fitted to predict percent change in MBL volume from Baseline (as a dependent variable) through the fixed-effects associated with covariates (ie, stratification factors of Baseline MBL volume and geographic region, visit, treatment, and visit by treatment interaction) and random effects (from the individual patients). In this model, an unstructured variance-covariance matrix is assumed for each patient.

See sample SAS codes below for illustration where PCHG_MBL is percent change in MBL volume from Baseline as a dependent variable, PID is patient identification number, BMBL is a randomization stratification factor (Baseline MBL < 225 vs \geq 225), REGION is a randomization stratification factor (North America vs Rest of World), TRT is treatment group (relugolix + E2/NETA or Placebo), VISIT is visit time point (4, 8, 12, 16, 20, and 24 weeks) and TRT*VISIT is the visit by treatment interaction. The specification of type=UN implements unstructured variance-covariance matrix for an individual patient with multiple measures of MBL volumes.

```
proc mixed data=MBL_dataset method=REML covtest;
  class PID BMBL REGION TRT VISIT;
  model PCHG_MBL= BMBL REGION VISIT TRT VISIT*TRT/s outp=ufmi_mixed_p
  covb;
  repeated VISIT /type=UN subject=PID r;
  lsmeans TRT/diff;
  ods output SolutionF=mixparms CovB=mixcovb;
```

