a maximum pain score ≥ 4 during the 35 days prior to randomization without restricting number of days of pain scores recorded in the e-Diary.

The analysis for endpoint 5 (proportion of women who achieve a maximum NRS score ≤ 1 for uterine fibroid-associated pain over the last 35 days of treatment in the subset of women with a maximum pain score ≥ 4 during the 35 days prior to randomization) will also be performed using NRS scores reported on eDiary during menstrual and non-menstrual days.

For key secondary efficacy endpoints (6 and 7) evaluating percent change from Baseline in uterine fibroid volume and uterine volume that are measured only at Week 24, an analysis of covariance (ANCOVA) model will be used to assess treatment effect with treatment, randomization stratification factors and Baseline value as covariates.

For key secondary efficacy endpoints (2 and 3) evaluating the change (absolute or % change) from Baseline to Week 24, treatment comparisons will be performed using a mixed model repeated measures approach with treatment, visit, randomization stratification factors and treatment by visit interactions included as fixed effects and random effects (from the individual patients). In this model, an unstructured variance-covariance matrix is assumed for each patient.

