7.4.2. Other Secondary Efficacy and Exploratory Endpoints

The following describes the analysis methods for other secondary efficacy endpoints and exploratory endpoints. There are three types of analyses corresponding to the three types of endpoints (time-to-event, continuous and binary) (see [Appendix 1](#) for details).

Time-to-Event Endpoint

For time to achieving an MBL volume of < 80 mL AND at least a 50% reduction from Baseline MBL volume (as an event), time to event will be defined as weeks from date of first dose of study drug to response (event) based on the MBL volume as assessed by the alkaline hematin method. The missing data handling rules described in Section [7.3.5](#) for deriving responder status at Week 24/EOT will be applied similarly at Weeks 8, 12, 16, and 20. Patients without an event will be censored at the last assessment date prior to the last dose of the study drug.

Kaplan-Meier methods will be used to describe the time to event distributions. A log-rank test stratified by the randomization stratification factors using the proportional hazard model (p-value from score test) will be used to compare relugolix + E2/NETA to placebo. Randomization stratification factors will be used to stratify inferential testing.

Continuous Endpoints

For endpoints evaluating the change (absolute or percent change) from Baseline to Week 24, treatment comparisons will be performed using a mixed model repeated measures approach with treatment, randomization stratification factors, visit, and treatment by visit interactions included as fixed effects. The Baseline value will be included as a covariate, and an unstructured variance-covariance matrix will be assumed. Calculation of the dependent variable (change from Baseline) for each patient at each visit will be calculated based on the visit windows specified in Section [4.3.5](#). Based on this model, the least squares mean at Week 24 will be compared between treatment groups and summarized along with the corresponding 95% CIs for treatment difference. In addition, summary statistics (mean change or mean % change) will be graphically presented as appropriate.

Binary Endpoints

For endpoints evaluating proportions, treatment comparisons will be performed using a stratified Cochran-Mantel-Haenszel test as appropriate with the randomization stratification factors as strata. Point estimates and 2-sided 95% CIs for treatment differences in proportions will be provided.

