A mixed-effects model with repeated measures will be used to describe treatment effect on BMD at 12 and 24 weeks. The model will have treatment group, age at Baseline, visit, Baseline BMD value, stratification factors (geographic region and menstrual blood loss volume), race (African American versus Other), and BMI at Baseline as fixed effects using an unstructured variance-covariance matrix. Least square means on each anatomical location will be presented and plotted at each visit with associated 95% CIs. Categorical representation of percentage change from Baseline to 12 and 24 weeks of treatment will be presented by the number and proportion of patients who had BMD declines of $\leq 2\%$, $> 2\%$ to 3% , $> 3\%$ to 5% , $> 5\%$ to 8% , and $> 8\%$ by treatment group and anatomical location. The 95% CIs will be provided for the respective proportions.

Categorical changes from Baseline in overall BMD (defined as lumbar spine and total hip) also will be assessed at 12 and 24 weeks. Femoral neck evaluates a smaller area of bone mass than the total hip and is prone to lower precision in the measurement ([ISCD Official Positions, 2015](#); [Leslie, 2007](#)). Since femoral neck BMD may be associated with discordant readings compared with the total hip or lumbar spine due to technical considerations, it will not add meaningful interpretation of overall BMD changes in response to treatment.

Z-scores will be summarized by treatment group, visit, and anatomical location with descriptive statistics including 95% CIs, and the number and percentage of patients with a Z-score < -2.0 will be presented by treatment group, visit, and anatomical location.

BMD percentage changes from Baseline will also be summarized by intrinsic factors (eg, age, race, body mass index) and extrinsic factors (eg, geographic region).

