Change from Baseline to Week 24 in the UFS-QoL Symptom Severity Scale score	mITT	Mixed-effects model	P < 0.05	Week 12, 24	LS means for change
Change from Baseline to Week 24 in the UFS-HRQL total score	mITT	Mixed-effects model	P < 0.05	Week 12, 24	LS means for change
Change in PGA for uterine fibroid related function from Baseline to Week 24	mITT	Mixed-effects model	P < 0.05	Monthly	LS means for absolute and change
Change in PGA for uterine fibroid symptoms from Baseline to Week 24	mITT	Mixed-effects model	P < 0.05	Monthly	LS means for absolute and change
Proportion of patients achieving improvement in PGA for uterine fibroid symptoms from Baseline to Week 24	mITT	Cochran-Mantel-Haenszel test	P < 0.05	Monthly	Frequency and percentages
Proportion of patients achieving improvement in PGA for uterine fibroid related function from Baseline to Week 24	mITT	Cochran-Mantel-Haenszel test	P < 0.05	Monthly	Frequency and percentages
Safety Related Endpoints					
% Change from Baseline to Week 12 in BMD (pooled data)	Safety population	Mixed-effects model Relugolix Group A vs B	P < 0.05	Week 12	LS means Diff (95%CI)

Secondary Endpoints	Analysis Population	Statistical Method/Test	Declare Statistical Significance ^a	Time Points of Summary	Summary Statistics
% Change from Baseline in BMD	Safety population	Mixed-effects model Relugolix Group A vs Placebo at 12/24 weeks; Relugolix Group B vs Placebo at 12 weeks		Week 12, 24	LS means Diff (95%CI)
Exploratory Secondary Efficacy Endpoints					
Change from Baseline to Week 24 in the Menorrhagia Impact Questionnaire Score for physical activities	mITT	Descriptive		Monthly	Frequency and percentages
Change from Baseline to Week 24 in the Menorrhagia Impact Questionnaire Score for social and leisure activities	mITT	Descriptive		Monthly	Frequency and percentages

Abbreviations: KM, Kaplan-Meier; LS, least squares; mITT, modified intent-to-treat; NRS, Numerical Rating Scale; Q, question; UFS-HRQL, Uterine Fibroid Scale – Health-related Quality of Life.

^a P-values are two-sided.

APPENDIX 2. DERIVATION AND PSYCHOMETRIC EVALUATION OF A UFS-QOL BLEEDING AND PELVIC DISCOMFORT SCALE

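### The BMD repeated-measures model in SAP 9.3.5 omits treatment-by-visit, so its adjusted between-arm differences are forced to be identical at Weeks 12 and 24

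*SAP*

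**What the plan says.** Section 9.3.5 gives the purpose of the model: "A mixed-effects model with repeated measures will be used to describe treatment effect on BMD at 12 and 24 weeks". It then lists the fixed effects: "The model will have treatment group, age at Baseline, visit, Baseline BMD value, stratification factors (geographic region and menstrual blood loss volume), race", followed by BMI at Baseline, with an unstructured covariance matrix. The list contains no interaction. The output asked for is visit-specific: "Least square means on each anatomical location will be presented and plotted at each visit with associated 95% CIs". Appendix 1, under the safety-related endpoints, assigns these contrasts to the model, to be reported as LS-mean differences with 95% CIs: "Mixed-effects model Relugolix Group A vs Placebo at 12/24 weeks; Relugolix Group B vs Placebo at 12 weeks".

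The SAP's other specified repeated-measures models do name the interaction. Section 7.3.6 (imputation of menstrual blood loss) lists "visit, treatment, and visit by treatment interaction" and repeats the term in its SAS code. Section 7.4.1 includes it for key secondary endpoints 2 and 3. Section 7.4.2 has "treatment, randomization stratification factors, visit, and treatment by visit interactions included as fixed effects". The version of the SAP that preceded Amendment 1 has the same BMD list, so the amendment did not change it.

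Section 2.1 describes Group B as "relugolix 40 mg once daily for 12 weeks followed by relugolix 40 mg once daily co-administered with E2 1 mg/NETA 0.5 mg for 12 weeks".

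**The concern.** A repeated-measures model with treatment and visit only as main effects estimates one difference per pair of arms. Its LS-mean curves over visits are parallel whatever the data show. It therefore cannot give separate Week 12 and Week 24 effects, which is what 9.3.5 and Appendix 1 ask of it.

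Equal differences at the two visits are not a safe assumption here. BMD change may accrue over time, and Group B's regimen changes at Week 12, between the two assessments. Its Week 12 contrast with placebo is the one that reflects relugolix without E2/NETA, and the constraint would mix post-switch data into it. The error can run either way, making bone loss look smaller or larger than it was at a given visit.

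There is a smaller related mismatch. The Table 1 objective compares both E2/NETA regimens with placebo on BMD change to Week 24, but 9.3.5 and Appendix 1 plan Group B versus placebo only at Week 12 and give no reason.

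**Working it through.** **The plan's own BMD figure.** Section 2.2.2 assumes 260 per group pooled over both studies, a 1.25% difference, SD 4% and 15% dropout. Evaluable per group: 260 x 0.85 = 221. SE = 4 x sqrt(2/221) = 0.381, and 1.25/0.381 - 1.96 = 1.325, giving 90.7% power (90.6% with the t distribution). The stated 90% reproduces. The concern does not depend on it.

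**Algebra.** As written, E[Y(g,v)] = mu + treatment(g) + visit(v) + covariates. For arms g and h at visit v, LSmean(g,v) - LSmean(h,v) = treatment(g) - treatment(h), which does not contain v. The unstructured covariance concerns residuals, not means, so it does not relax this. No effect sizes need to be assumed. LS means may still differ between visits through the visit term; only the between-arm differences are forced equal.

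**What the single number estimates.** Inputs:
- 130 per arm (2.2.1), less 15% dropout at Week 12 (2.2.2): 130 x 0.85 = 110.5, taken as 110.
- Less 20% by Week 24 (2.2.1): 130 x 0.80 = 104.
- SD 4% (2.2.2, stated for Week 12). Applying it at Week 24 is an assumption.
- Within-patient correlation r from 0.3 to 0.8 (assumed).

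With monotone dropout, the information per arm on the two visit means is I = 104 x Sigma^-1, plus (110 - 104)/16 in the Week 12 diagonal cell. The weights on the two visit-specific differences are the row sums of I divided by their total. With SD 4 at both visits each row sum of Sigma^-1 is 1/[16(1 + r)], so:

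| r | Week 12 row sum | Week 24 row sum | Weights (Week 12 / Week 24) |
|---|---|---|---|
| 0.3 | 5.000 + 0.375 = 5.375 | 5.000 | 0.518 / 0.482 |
| 0.6 | 4.0625 + 0.375 = 4.4375 | 4.0625 | 0.522 / 0.478 |
| 0.8 | 3.611 + 0.375 = 3.986 | 3.611 | 0.525 / 0.475 |

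**Illustrations** (true effects assumed, not in the SAP; weights at r = 0.6):
- Group A minus placebo -0.5% then -1.0%: 0.522 x (-0.5) + 0.478 x (-1.0) = -0.74% at both visits.
- Group A minus placebo -1.0% then -0.5%: -0.76% at both.
- Group B minus placebo -2.0% then -1.5%: -1.76% at both. With -2.0% then -2.5%: -2.24% at both.
- Equal true differences: no bias.

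**If the Week 24 SD is larger** (5%, assumed), the Week 24 row sum of I is 104 x 10/364 = 2.857 at r = 0.3, against 104 x 19/364 + 0.375 = 5.804 for Week 12, so the Week 24 weight is 0.33. At r = 0.8 the Week 24 row sum is 0 and so is the weight. The first example then reads between -0.67% and -0.50% against a true Week 24 value of -1.0%.

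**Simulation check.** 400 three-arm trials, SD 4, r = 0.6, true A minus placebo -0.5/-1.0 and B minus placebo -2.0/-1.5. The main-effects model returned -0.72 and -1.73 at both visits (Monte Carlo SE 0.024). With the interaction it returned -0.46/-0.99 and -1.98/-1.47 (Monte Carlo SE 0.026-0.027).

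**Precision.** At r = 0.6 the common-effect SE is sqrt(2/8.5) = 0.485. The visit-specific SEs are sqrt(2 x 16/110) = 0.539 at Week 12 and sqrt(2 x [16 x 0.64/104 + 0.36 x 16/110]) = 0.549 at Week 24. The ratios are 1.11 and 1.13. Over r from 0.3 to 0.8 the common-effect SE runs from 0.44 to 0.51, and the widening from 26% (r = 0.3) down to 5% (r = 0.8).

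**The case against.** The best defence is that the list is incomplete, not deliberately additive. The same paragraph asks for the effect at two time points and Appendix 1 wants different contrasts at different weeks, so the interaction must have been intended. Nor are the SAP's model lists uniformly complete: 7.4.2 names the Baseline value as a covariate and 7.4.1 does not. That is a fair reading of intent, but the text does not say it. The BMD list is detailed down to race coding and BMI, the other repeated-measures models spell the term out, and 7.4.2 covers efficacy and exploratory endpoints, so it does not supply the term to BMD. A programmer following 9.3.5 would fit main effects.

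Four points on reach stand:
- Section 9.3.5 also plans between-group differences at each visit with CIs and names no model for them. If computed directly from observed changes, they are correct and would sit beside the modelled ones. If taken from the model, as Appendix 1 suggests, they share the defect.
- The formal pooled A versus B test at Week 12 is specified in the Integrated Summary of Safety SAP, which is not shown. It is affected only if that plan uses the same terms.
- The placebo contrasts carry no significance criterion in Appendix 1, so no formal decision in this SAP turns on them.
- The effect sizes and the 5% SD are assumptions. In the SD 4% examples the distortion is 0.24 to 0.26 points, under half a visit-specific SE.

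On Group B versus placebo at Week 24, both arms' Week 24 changes are reported anyway, so only the contrast is missing. The limit on Group B testing in 7.2 sits among the efficacy comparisons and does not exclude it.

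**Conclusion.** The concern holds. As written, the model gives one adjusted difference per pair of arms and cannot produce the visit-specific differences that 9.3.5 and Appendix 1 ask for. This is algebraic and rests on no assumed effect. The size of the error depends on how far the true Week 12 and Week 24 differences diverge. With SD 4% at both visits and 110/104 patients per arm, each visit's reported difference is off by about half of that divergence; with a larger SD at Week 24, the Week 24 figure can be off by nearly all of it. The bias is zero only if the two true differences are equal.

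The damage is confined to the adjusted BMD safety estimates in the study reports. It should be fixed before the analysis is run, but it does not touch the efficacy conclusions. The missing Group B versus placebo contrast at Week 24 is a minor addition to the same point.

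**What to change.** Add treatment-by-visit to the fixed effects of the BMD model in 9.3.5, and take the LS means and LS-mean differences at Weeks 12 and 24 from that term. State whether the by-visit between-group differences in 9.3.5 come from this model or directly from observed changes. Add the Group B versus placebo difference at Week 24 to 9.3.5 and Appendix 1 so that they match the Table 1 objective, or say in one sentence why it is left out. Check that the Integrated Summary of Safety SAP includes the interaction if it uses a repeated-measures model.

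The cost is one model term plus one contrast or one sentence. The wider intervals quantified above are the price of estimating each visit separately, and no additional data are needed.

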APPENDIX 1. SUMMARY OF SECONDARY ENDPOINT ANALYSES

Secondary Endpoints	Analysis Population	Statistical Method/Test	Declare Statistical Significance ^a	Time Points of Summary	Summary Statistics
Key Secondary Efficacy Endpoints with Alpha Protection					
Proportion of women who achieve amenorrhea over the last 35 days of treatment	mITT	Cochran-Mantel-Haenszel test	P < 0.05	Week 24	Frequency and percentages
% change from Baseline to Week 24 in MBL volume	mITT	Mixed-effects model	P < 0.05	Week 24	LS means for % change
Proportion of women with a hemoglobin ≤ 10.5 g/dL at Baseline who achieve an increase of > 2 g/dL from Baseline at Week 24	Subset of mITT	Cochran-Mantel-Haenszel test	P < 0.05	Week 24	Frequency and percentages
Change from Baseline to Week 24 in the UFS-QoL Bleeding and Pelvic Discomfort Scale score, a sub-scale of the UFS-QoL Symptom Severity Scale	mITT	Mixed-effects model	P < 0.05	Week 24	LS means for change
Proportion of patients with a maximum NRS score ≤ 1 during the 35 days before the last dose of study drug in the subset of women with a maximum NRS score ≥ 4 for pain associated with uterine fibroids during the 35 days prior to randomization	Subset of mITT	Cochran-Mantel-Haenszel test	P < 0.05	Week 24/EOT	Frequency and percentages
% change from Baseline to Week 24 in uterine fibroid volume	mITT	ANCOVA model	P < 0.05	Week 24	LS means for % change
% change from Baseline to Week 24 in uterine volume	mITT	ANCOVA model	P < 0.05	Week 24	LS means for % change
Other Secondary Efficacy Endpoints					
Time to achieve MBL volume of < 80 mL AND at least a 50% reduction from Baseline MBL volume as measured by the alkaline hematin method	mITT	Log-rank test/KM method	P < 0.05	Monthly	KM estimates at Week 12 and 24, KM plots, median time to response
Time to achieve amenorrhea	mITT	Log-rank test/KM method	P < 0.05	Monthly	KM plots, median time to response

Secondary Endpoints	Analysis Population	Statistical Method/Test	Declare Statistical Significance ^a	Time Points of Summary	Summary Statistics
Time to sustained amenorrhea	mITT	Log-rank test/KM method	P < 0.05	Monthly	KM plots, median time to response
Proportion of women in the relugolix Group A versus the placebo Group C who achieve an MBL volume of < 80 mL AND at least a 50% reduction from Baseline MBL volume at Week 4, Week 12, Week 16, and Week 20	mITT	No comparison		at Week 4, Week 12, Week 16, and Week 20	Descriptive
Sustained amenorrhea rate by visit	mITT	Cochran-Mantel-Haenszel test	P < 0.05	Monthly	Frequency and percentages
Proportion of women with a hemoglobin below the lower limit of normal at Baseline who achieve an increase of ≥ 1 g/dL from Baseline at Week 24	mITT	Cochran-Mantel-Haenszel test	P < 0.05	Monthly	Frequency and percentages
Change (absolute and %) from Baseline to Week 24 in hemoglobin for women with a hemoglobin ≤ 10.5 g/dL at Baseline	mITT	Mixed-effects model	P < 0.05	Monthly	LS means for % change
Proportion of women who achieve a maximum Numerical Rating Scale score for uterine fibroid-associated pain over the last 35 days of treatment that is at least a 30% reduction from Baseline in the subset of women with a maximum pain score ≥ 4 during the 35 days prior to randomization	Subset of mITT	Cochran-Mantel-Haenszel test	P < 0.05	Week 12, 24	Frequency and percentages
Mean maximum NRS scores over time	Subset of mITT	Descriptive		Monthly	Means
Proportion of responders who had meaningful reduction of >20 points from Baseline to Week 24 in UFS-QOL Bleeding and Pelvic Discomfort Scale (Q1, Q2 and Q5)	mITT	Cochran-Mantel-Haenszel test	P < 0.05	Week 12, 24	Frequency and percentages
Proportion of responders who had meaningful increase of > 20 points from Baseline to Week 24 in UFS-QOL revised activities	mITT	Cochran-Mantel-Haenszel test	P < 0.05	Week 12, 24	Frequency and percentages

Secondary Endpoints	Analysis Population	Statistical Method/Test	Declare Statistical Significance ^a	Time Points of Summary	Summary Statistics
Change from Baseline to Week 24 in impact of uterine fibroids based on the UFS-QOL revised activities domain	mITT	Mixed-effects model	P < 0.05	Week 12, 24	LS means for change
Change from Baseline to Week 24 in impact of uterine fibroids based on the UFS-QOL activities domain	mITT	Mixed-effects model	P < 0.05	Week 12, 24	LS means for change
Change from Baseline to Week 24 in the interference of uterine fibroids with physical activities based on UFS-QOL Q11	mITT	Mixed-effects model	P < 0.05	Week 12, 24	LS means for change
Change from Baseline to Week 24 in the interference of uterine fibroids with social activities based on UFS-QOL Q20	mITT	Mixed-effects model	P < 0.05	Week 12, 24	LS means for change
Change from Baseline to Week 24 in embarrassment caused by uterine fibroids based on UFS-QOL Q29	mITT	Mixed-effects model	P < 0.05	Week 12, 24	LS means for change
Change from Baseline to Week 24 in the UFS-QoL Symptom Severity Scale score	mITT	Mixed-effects model	P < 0.05	Week 12, 24	LS means for change
Change from Baseline to Week 24 in the UFS-HRQL total score	mITT	Mixed-effects model	P < 0.05	Week 12, 24	LS means for change
Change in PGA for uterine fibroid related function from Baseline to Week 24	mITT	Mixed-effects model	P < 0.05	Monthly	LS means for absolute and change
Change in PGA for uterine fibroid symptoms from Baseline to Week 24	mITT	Mixed-effects model	P < 0.05	Monthly	LS means for absolute and change
Proportion of patients achieving improvement in PGA for uterine fibroid symptoms from Baseline to Week 24	mITT	Cochran-Mantel-Haenszel test	P < 0.05	Monthly	Frequency and percentages
Proportion of patients achieving improvement in PGA for uterine fibroid related function from Baseline to Week 24	mITT	Cochran-Mantel-Haenszel test	P < 0.05	Monthly	Frequency and percentages
Safety Related Endpoints					
% Change from Baseline to Week 12 in BMD (pooled data)	Safety population	Mixed-effects model Relugolix Group A vs B	P < 0.05	Week 12	LS means Diff (95%CI)

Secondary Endpoints	Analysis Population	Statistical Method/Test	Declare Statistical Significance ^a	Time Points of Summary	Summary Statistics
% Change from Baseline in BMD	Safety population	Mixed-effects model Relugolix Group A vs Placebo at 12/24 weeks; Relugolix Group B vs Placebo at 12 weeks		Week 12, 24	LS means Diff (95%CI)
Exploratory Secondary Efficacy Endpoints					
Change from Baseline to Week 24 in the Menorrhagia Impact Questionnaire Score for physical activities	mITT	Descriptive		Monthly	Frequency and percentages
Change from Baseline to Week 24 in the Menorrhagia Impact Questionnaire Score for social and leisure activities	mITT	Descriptive		Monthly	Frequency and percentages

Abbreviations: KM, Kaplan-Meier; LS, least squares; mITT, modified intent-to-treat; NRS, Numerical Rating Scale; Q, question; UFS-HRQL, Uterine Fibroid Scale – Health-related Quality of Life.

^a P-values are two-sided.

APPENDIX 2. DERIVATION AND PSYCHOMETRIC EVALUATION OF A UFS-QOL BLEEDING AND PELVIC DISCOMFORT SCALE

The BPD Scale was derived from the Symptom Severity Scale of the Uterine Fibroid Symptom and Health-Related Quality of Life (UFS-QoL). The BPD Scale consists of three items proximal to uterine fibroids that are experienced by most patients, (ie, heavy bleeding during the menstrual period [Question 1], passing blood clots during the menstrual period [Question 2], and feeling tightness or pressure in the pelvic area [Question 5]).

The aim of this appendix is to describe the derivation and psychometric testing process of the BPD Scale. Results of the analyses in this appendix are summarized in [Appendix 3](#) and will be included in the Patient-Reported Outcomes dossier to be submitted at the time of filing for the uterine fibroids registration program.

Exploratory factor analysis and subsequent confirmatory factor analysis were conducted to assess and confirm the factor structure of the Symptom Severity Scale of the UFS-QoL, using data from a phase 2 study of relugolix in uterine fibroids (TAK-385/CCT-001), as well as pooled, blinded data from one-third of patients in the phase 3 studies (MVT-601-3001 and MVT-601-3002). Respective analyses are described in [Section 2.1](#). Based on the results, the factor(s) reflecting symptoms proximal to uterine fibroids and experienced by most patients with uterine fibroids were selected for further psychometric testing.

The psychometric properties of the new scale were assessed using the same pooled, blinded data from the two phase 3 studies of relugolix in uterine fibroids (MVT-601-3001 and MVT-601-3002). These analyses are described in [Section 2.2](#). The blinded data consists of the first third of patients (approximately $n = 260$) enrolled into the two pivotal studies who have completed the patient global assessment (PGA) for symptoms and the UFS-QoL at Baseline and at Week 24. Of note, for the analyses specified in [Section 2.2](#), only data at Baseline and Week 12 were used; the Week 24 data was used in the responder analyses described in [Appendix 3](#).

2.1. Development of the Bleeding and Pelvic Discomfort Scale Using Phase 2 and Phase 3 Data

From a review of the eight items in the Symptom Severity Scale of the UFS-QoL, it was apparent that the scale consists of different constructs/dimensions. Therefore, the factor structure of the Symptom Severity Scale was assessed, initially using data from the phase 2 study TAK-385/CCT-001 ($n = 216$).

Of note, in the TAK-385/CCT-001 phase 2 study, the UFS-QoL with a one-month recall period was applied, whereas the UFS-QoL with a three-month recall period is used in the phase 3 studies (MVT-601-3001 and MVT-601-3002). Therefore, confirmatory factor analysis and final psychometric testing of the chosen factor was conducted using blinded phase 3 data (see [Section 2.2](#)).

Exploratory Factor Analysis

The exploratory factor analysis was done on phase 2 data to identify the underlying constructs by the most parsimonious factor structure of the eight items in the Symptom Severity Scale.

Identification of the number of factors was based on the following criteria:

- Items with primary factor loading > 0.4 ;
- Factors with large eigenvalues considered as common factors using Kaiser criterion ([Kaiser, 1960](#)).

A scree plot was used as a supplemental tool to decide on the number of factors in the final model.

Confirmatory Factor Analysis

Once the number of factors was identified, a confirmatory factor analysis was conducted using blinded, pooled phase 3 data to confirm the factor structure. Only patients who completed the Baseline and Week 24 PGA for symptoms and UFS-QoL assessments were included in this analysis. Model fit was assessed based on the following:

- The goodness of fit as measured by χ^2 and Goodness of Fit Index; a Goodness of Fit Index > 0.9 is considered acceptable;
- The Comparative Fit Index was used to determine the acceptability of the model fit of the discrepancy function adjusted sample size; a Comparative Fit Index > 0.9 ([Hu, 1995](#)) was considered an acceptable fit;
- The root mean square error of approximation was used to determine the acceptability of model fit of the square root of the discrepancy between the sample covariance matrix and the model covariance matrix; the root mean square error of approximation had to be < 0.06 ([Browne, 1993](#)) to be considered an acceptable fit;
- P-value > 0.05 .

Once the final factor structure was identified, the factor reflecting items proximal to uterine fibroids and experienced by almost all patients with uterine fibroids were selected for further evaluation. Of note, this was the BPD Scale.

